3.7. GCLLSG CLL Registry

Consenting subjects for inclusion in the GCLLSG registry is requested at screening or as close thereafter as possible.

3.8. Post Study Care

At this time, there is no plan to provide post-study care to subjects who have participated in this study.

4. SUBJECT POPULATION

4.1. Number of Subjects

The study will enroll approximately 36 subjects in total; 30 evaluable subjects in Arm B and approximately 6 subjects in Arm A.

4.2. Inclusion Criteria

Subjects must meet all the following criteria to be eligible for participation in this study:

- 1) Documentation of relapsed or refractory CLL
- 2) Have an indication per modified IWCLL 2008 criteria for treatment; subjects without radiographically measurable disease (defined as ≥ 1 lesion > 1.5 cm in diameter as assessed by CT or MRI) must have bone marrow evaluation at screening
- 3) Adequate hematologic function as indicated by a platelet count $\geq 50 \times 10^9/L$, a neutrophil count $\geq 1 \times 10^9/L$ and a hemoglobin ≥ 8 g/dL unless lower values are directly attributable to documented bone marrow burden of CLL
- 4) Adequate renal function as indicated by a CrCl ≥ 50 mL/min calculated by the modified Cockcroft-Gault formula or from a 24 hour urine collection
- 5) Adequate liver function as indicated by total bilirubin $\leq 1.5 \times$ institutional upper limit of normal (ULN) unless attributed to Gilbert's syndrome and AST/ALT $\leq 2.5 \times$ ULN
- 6) Male or female ≥ 18 years of age
- 7) Eastern Cooperative Oncology Group (ECOG) Performance Status (PS) ≤ 2
- 8) Absence of active HBV infection (serological testing within 6 weeks prior to randomization or enrollment with the following results: HBsAg negative AND anti-HBcAb negative, or if anti-HBcAb positive, HBV DNA PCR negative)
- 9) HCV Ab negative or if Ab positive, negative HCV RNA PCR within 6 weeks prior to randomization or enrollment
- 10) Negative testing for HIV within 6 weeks prior to randomization or enrollment
- 11) Satisfies the following criteria:
 - a) For female subjects of childbearing potential, willingness to abstain from sexual intercourse or use a protocol-specified method of contraception as described in [Appendix 4](#)
 - b) Male subjects of reproductive potential who engage in sexual intercourse must agree to use protocol-specified method(s) of contraception as described in [Appendix 4](#)

- 12) Ability and willingness to provide written informed consent and adhere to protocol requirements including study visit schedule, drug administration plan, imaging studies, laboratory testing, other study procedures and restrictions including mandatory prophylaxis for PJP

4.3. Exclusion Criteria

Subjects who meet any of the following exclusion criteria are not eligible for participation in this study:

- Known transformation of CLL (ie, Richter's transformation, prolymphocytic leukemia)
- Known CNS involvement
- Progression on treatment with any inhibitor of BTK, SYK, PI3K, BCL-2, or obinutuzumab. The treatment and disease response history of subjects with prior treatment with agents in these classes should be reviewed by the sponsor or the GCLLSG study office centrally prior to enrollment to clarify sensitivity to these treatments.
- Any treatment for CLL other than corticosteroids for symptomatic management within 28 days of the start of study treatment
- Participation on a concurrent therapeutic clinical trial unless all treatment is complete with only ongoing surveillance
- Diagnosis of or concern for progressive multifocal leukoencephalopathy
- History of myelodysplastic syndrome or another malignancy other than CLL, *except* for the following: any malignancy that has been in complete remission for 3 years, adequately treated local basal cell or squamous cell carcinoma of the skin, cervical carcinoma in situ, superficial bladder cancer, asymptomatic prostate cancer without known metastatic disease and with no requirement for therapy or requiring only hormonal therapy and with normal prostate-specific antigen for ≥ 1 year prior to start of study therapy
- Active infection requiring systemic therapy
- Pregnant or nursing women (a negative pregnancy test is required for all women of childbearing potential within 7 days before start of treatment and monthly during therapy)
- Active autoimmune disease including autoimmune hemolytic anemia or idiopathic thrombocytopenic purpura requiring a higher corticosteroid equivalent than prednisone 10 mg daily. Higher doses of corticosteroids prescribed for any indication must be stopped >14 days prior to randomization or enrollment; exceptions may be made for corticosteroids prescribed specifically for management of CLL symptoms after discussion with the study medical monitor.

- Diagnosis of inflammatory bowel disease or ongoing symptomatic pneumonitis
- Ongoing CMV infection, treatment or prophylaxis for CMV within the past 28 days
- History of stroke or intracranial hemorrhage within 12 months of randomization or enrollment; subjects requiring therapeutic anticoagulation for any indication should be discussed with the GCLLSG coordinating physician and/or medical monitor prior to screening
- Legal incapacity, prisoners or subjects institutionalized by regulatory or court order, or any individual in dependence to study sponsor or any investigator
- Use of a strong CYP3A4 or a strong P-gp inducer within 2 weeks of first dose of study treatment or anticipated chronic use while on study
- Demonstration of QTc interval > 450 milliseconds or requirement for ongoing treatment with concomitant medications that prolong the QT interval
- Known hypersensitivity to obinutuzumab, idelalisib, tirabrutinib, or any of the excipients

5. INVESTIGATIONAL MEDICINAL PRODUCTS

5.1. Randomization

It is the responsibility of the Investigator to ensure that subjects are eligible for the study prior to randomization or enrollment. Subjects will be assigned a unique screening number at the time of consent. A medical review of selected screening data will be performed by members of the GCLLSG to confirm eligibility and must be completed prior to randomization or enrollment.

Once eligibility is confirmed, subjects will be assigned a unique subject number from the interactive web response system (IWRS), randomized in a 1:1 ratio to treatment with the combination of tirabrutinib and idelalisib with and without obinutuzumab. The randomization will be stratified by the presence of del17p/TP53mut in CLL cells. Once a subject number is assigned to a subject, it will not be reassigned to another subject. This is an open-label study.

With Amendment 3, randomization of subjects will no longer be performed as only Arm B of the study will continue to enroll.

All Day 1 tests and procedures must be completed prior to the dispensation and administration of the first dose of study treatment on Week 1 Day 1.

5.2. Description and Handling of Tirabrutinib, Idelalisib, and Obinutuzumab

5.2.1. Tirabrutinib

5.2.1.1. Formulation

Tirabrutinib film-coated tablets, 20 mg, contain the equivalent of 20 mg tirabrutinib as the hydrochloride salt (GS-4059-01) and utilize a 10% w/w drug load formulation. The 20 mg tablet is a blue, plain-faced, round, film-coated tablet and contains the following inactive ingredients: lactose monohydrate, microcrystalline cellulose, crospovidone, colloidal silicon dioxide, magnesium stearate, polyvinyl alcohol, titanium dioxide, polyethylene glycol, talc, and FD&C blue #2/indigo carmine aluminum lake.

Tirabrutinib film-coated tablets, 40mg, contain the equivalent of 40 mg tirabrutinib as the hydrochloride salt (GS-4059-01). The 33% drug load formulation tablet is an orange, plain-faced, round, film-coated tablet. The tirabrutinib film-coated tablets, 40 mg, contain the following inactive ingredients: lactose monohydrate, microcrystalline cellulose, crospovidone, colloidal silicon dioxide, magnesium stearate, polyvinyl alcohol, titanium dioxide, polyethylene glycol, talc, FD&C yellow #6/sunset yellow FCF aluminium lake, and iron oxide yellow.

Tirabrutinib film-coated tablets, 80 mg, contain the equivalent of 80 mg tirabrutinib as the hydrochloride salt (GS-4059-01) and utilize a 33% drug load formulation. The 80 mg tablet is a yellow, plain-faced, modified capsule-shaped, film-coated tablet and contains the following inactive ingredients: lactose monohydrate, microcrystalline cellulose, crospovidone, colloidal silicon dioxide, magnesium stearate, polyvinyl alcohol, titanium dioxide, polyethylene glycol, talc, and iron oxide yellow.

5.2.1.2. Packaging and Labeling

Tirabrutinib tablets are packaged in white, HDPE bottles. Each bottle contains 30 tablets, silica gel desiccant and polyester packing material. Each bottle is enclosed with a white, continuous thread, child-resistant polypropylene screw cap with an induction-sealed and aluminum-faced liner.

Study drug(s) shall be labeled to meet applicable requirements of the EU Guideline to Good Manufacturing Practice Annex 13 (Investigational Medicinal Products) and/or other local regulations.

5.2.1.3. Storage and Handling

Study drug tirabrutinib should be stored at controlled room temperature of 25°C (77°F); excursions are permitted between 15°C and 30°C (59°F and 86°F). Storage conditions are specified on the label. Until dispensed to the subjects, all bottles of study drugs should be stored in a securely locked area, accessible only to authorized site personnel. To ensure the stability and proper identification, study drug(s) should not be stored in a container other than the container in which they were supplied.

Consideration should be given to handling, preparation, and disposal through measures that minimize drug contact with the body. Appropriate precautions should be followed to avoid direct eye contact or exposure when handling.

5.2.2. Idelalisib

5.2.2.1. Formulation

Idelalisib will be provided in tablets intended for oral administration. Each tablet contains 100 mg of active idelalisib. The 100 mg tablets are oval, debossed with “100” on one side and “GSI” on the other, and film-coated orange. The tablets include the following inactive excipients: microcrystalline cellulose, hydroxypropyl cellulose, croscarmellose sodium, sodium starch glycolate, magnesium stearate, red iron oxide (50 mg tablets only), FD&C Yellow #6/Sunset Yellow FCF aluminum lake (100 mg tablets only), polyethylene glycol, talc, polyvinyl alcohol (PVA), and titanium dioxide.

5.2.2.2. Packaging and Labeling

Idelalisib tablets are packaged in white, HDPE bottles. Each bottle contains 60 tablets and polyester packing material. Each bottle is enclosed with a white, continuous thread, child-resistant polypropylene screw cap with an induction-sealed and aluminum-faced liner.

Idelalisib to be distributed to centers in the EU shall be labeled to meet applicable requirements of the EU Guideline to Good Manufacturing Practice Annex 13 (Investigational Medicinal Products), and/or other local regulations.

5.2.2.3. Storage and Handling

Idelalisib bottles should be stored at controlled room temperature of 25°C (77°F); excursions are permitted between 15°C and 30°C (59°F and 86°F). Storage conditions are specified on the label. Until dispensed to the subjects, all bottles of study drugs should be stored in a securely locked area, accessible only to authorized site personnel. To ensure the stability and proper identification, study drug(s) should not be stored in a container other than the container in which they were supplied.

Consideration should be given to handling, preparation, and disposal through measures that minimize drug contact with the body. Appropriate precautions should be followed to avoid direct eye contact or exposure through inhalation when handling idelalisib.

5.2.3. Obinutuzumab

5.2.3.1. Formulation

Please refer to the Gazyvaro (obinutuzumab) SmPC.

5.2.3.2. Packaging and Labeling

Commercially available product of obinutuzumab will be used for this study.

Obinutuzumab to be distributed to centers in the EU shall be labeled to meet applicable requirements of the EU Guideline to Good Manufacturing Practice Annex 13 (Investigational Medicinal Products), and/or other local regulations.

5.2.3.3. Storage and Handling

Commercially available obinutuzumab will be used for this study. Further information regarding storage and handling are available in the Gazyvaro (obinutuzumab) SmPC.

5.3. Dosage and Administration of Tirabrutinib, Idelalisib, and Obinutuzumab

5.3.1. Tirabrutinib and Idelalisib

Tirabrutinib and idelalisib will be provided by Gilead. Tirabrutinib tablets (4 × 20 mg, 2 × 40 mg, or 1 × 80 mg) and idelalisib tablets (1 × 100 mg) will be self-administered orally once daily. Dosing with both agents will begin on Week 1 Day 1 of the study and thereafter at approximately the same time each day until end of treatment. Study drugs should be swallowed whole with water. Tirabrutinib and idelalisib may be administered without regard to food.

For patients assigned to the 20 mg tirabrutinib dose, 20 mg tirabrutinib tablets may be exchanged for 40 mg tirabrutinib tablets leading to an increase in total daily dose from 20 mg to 40 mg. Based on the range of exposures of tirabrutinib observed in subjects with B-cell malignancies, the slight increase in daily dose is not considered clinically relevant.

If the subject misses a dose, he/she should be instructed to take the study drug as soon as he/she remembers, unless more than 12 hours has elapsed since the scheduled time of the missed dose for study drugs administered once daily or 6 hours for study drugs administered twice daily. In this case, the subject should be instructed to wait and take the next dose at the regularly scheduled time.

5.3.2. Obinutuzumab

Liquid concentrate of obinutuzumab intended for IV infusion is prepared by diluting the drug product to the final concentration into an infusion bag containing 0.9 % Sodium Chloride (NaCl).

All patients should receive premedication before administration of obinutuzumab as follows:

First infusion of obinutuzumab

The following premedication should be administered (unless contraindicated) prior to the start of the first dosage of obinutuzumab (Days 1 [and 2 in case of dose splitting]) to avoid infusion related reactions (IRRs):

- Prednisolone or prednisone 100 mg IV \geq 1 hrs before starting the obinutuzumab infusion (an equivalent dose of dexamethasone [20 mg] or methylprednisolone [80 mg] is permitted, but hydrocortisone should not be used)
- Acetaminophen/paracetamol 1000 mg p.o. \geq 30 min before starting the obinutuzumab infusion
- Antihistamines including a H1-antagonist (eg, dimetindene 4 mg IV) and a H2-antagonist (eg, ranitidine 50 mg IV) \geq 30 min before starting the obinutuzumab infusion

Please note that withholding of antihypertensive treatments should be considered for 12 hours prior to, throughout, and for the first hour after each obinutuzumab infusion as hypotension may occur as a result of an IRR. Antihypertensive treatment can still be used to treat IRR triggered hypertension, if required.

Subsequent infusions of obinutuzumab

All patients should receive oral acetaminophen/paracetamol (1000 mg) p.o. \geq 30 min ahead of every obinutuzumab infusion (unless contraindicated). The antihistamine premedication may be omitted at the investigator's discretion for the following obinutuzumab infusions if the previously administered obinutuzumab infusion did not result in an IRR CTCAE Grade $>$ 1 (ie, no medication was required to treat the IRR and there was no interruption of the infusion). A corticosteroid should be administered for premedication if the patient experienced a Grade 3 IRR during the previous infusion, the patient's lymphocyte count is $>$ 25,000/ μ l and at the investigator's discretion. As during the first cycle, the investigator should consider withholding antihypertensive medication 12 hours prior and until 1 hour after the obinutuzumab infusion.

Patients with a history of cardiac disease should be monitored closely. In addition these patients should be hydrated with caution in order to prevent a potential fluid overload.

Patients with a high tumor burden (leukocyte counts $\geq 25 \times 10^9/L$ and/ or bulky lymphadenopathy) and/or renal impairment ($CrCl < 70$ mL/min) are at risk for developing a tumor-lysis syndrome (TLS). These patients with a high tumor burden and also all other patients considered at risk for TLS by the investigator must receive prophylaxis for TLS prior to the initiation of treatment with obinutuzumab and ahead of all subsequent administrations of obinutuzumab until the tumor burden is reduced and risk for development of a TLS is minimized. Possible preventive measures include:

- adequate hydration (eg, intravenous administration of 1000 – 4000 mL NaCl 0.9% starting 12 – 24 hours before treatment),
- prophylactic administration of an uric acid reducer (eg, allopurinol 300 mg once daily starting 12 – 24 hours prior to initiation of treatment) and/or
- rasburicase (*Fasturtec*[®]).

In addition, a close monitoring of serum chemistry, particularly creatinine, potassium and uric acid levels must be performed. Patients with TLS should be treated per institutional practice (including correction of electrolyte abnormalities, monitoring of renal function and fluid balance, administration of supportive care, including dialysis as indicated).

Infusion Rates

First infusion: All subjects will receive an infusion of the fixed dose of 100 mg obinutuzumab administered at a fixed rate of 25 mg/hr over 4 hours. If the first 100 mg obinutuzumab is tolerated well and completed without interruptions or adjustments of infusion rate and it is possible from an organizational and medical point of view (enough time, medical supervision available throughout the infusion), patients are allowed to continue with the remaining 900 mg infusion on the same day. Otherwise the remaining 900 mg should be infused the next day. The infusion with 900 mg obinutuzumab should be started at a rate of 50 mg/hr in all patients and the infusion rate may be escalated in increments of 50 mg/hr every 30 minutes to a maximum rate of 400 mg/hr.

Subsequent infusions: If the first infusion of obinutuzumab was well tolerated (defined by an absence of IRRs during a final infusion rate of ≥ 100 mg/hr), subsequent infusions will be administered at an initial rate of 100 mg/hr. The infusion rate may be increased by 100 mg/hr increments at 30-minute intervals, as tolerated, to a maximum rate of 400 mg/hr. Alternatively, if an IRR was present during the first infusion, the administration may be per the guidance from the first infusion with a maximum rate that which has been previously tolerated by the subject. At the investigator's discretion, obinutuzumab infusions may be split and administered over 2 days.

	Dose of Obinutuzumab	Rate of Infusion (in the absence of infusion reactions/hypersensitivity during previous infusions)
Day 1	100 mg	Administer at 25 mg/hr over 4 hours. Do not increase the infusion rate.
Day 1 or 2	900 mg	Administer at 50 mg/hr. The rate of the infusion can be escalated in increments of 50 mg/hr every 30 minutes to a maximum rate of 400 mg/hr.
Subsequent	1000 mg	Infusions can be started at a rate of 100 mg/hr and increased by 100 mg/hr increments every 30 minutes to a maximum of 400 mg/hr.

Management of infusion-related reactions (IRRs)

In case of IRR, the following measures should be considered depending on the severity of the IRR:

- Acetaminophen/paracetamol 1000 mg if not administered during the last 4 hrs
- Antihistamines including a H1- (eg, dimetindene 4 mg IV) and a H2-antagonist (eg, ranitidine 50 mg IV) if not administered during the last 4 hours
- Prednisolone or prednisone 100 mg IV in case of urticarial, bronchospasm and dyspnea
- Intravenous fluids
- Bronchodilators and oxygen in case of bronchospasm and dyspnea
- Vasopressors in case of hypotension

Once symptoms have resolved completely, obinutuzumab may be resumed at 50% of the infusion-rate used prior to the interruption. If no infusion related symptoms occur, the rate of the infusion may be escalated stepwise with 50 mg/hr every 30 minutes to a maximum rate of 400 mg/hr, except for the first administration of obinutuzumab. The first obinutuzumab administration (100 mg) may be re-started at half initial rate (12.5 mg/hr) upon complete resolution of symptoms; if this is tolerated well for an hour, the rate may be increased to a maximum of 25 mg/hr.

It needs to be stressed that in the event of a life-threatening (which may include pulmonary or cardiac events), prolonged or recurrent IRR, obinutuzumab should be discontinued immediately and no further obinutuzumab should be administered.

Patients experiencing Grade 3 or 4 IRRs twice should receive aggressive symptomatic treatment and will be discontinued from further study treatment with obinutuzumab. Treatment with oral agents should be continued with the subject remaining on study.

For guidance on the management of infusion-related reactions (IRRs) see the following table:

IRR Severity (NCI CTCAE v4.0)	Recommendation
Grade 1-2	Reduce the infusion rate or hold infusion Administer supportive treatment Upon symptom resolution, restart infusion at no more than half the previous rate (the rate being used at the time that the IRR occurred) and, if patient does not experience any IRR symptoms, infusion rate escalation may resume at the increments and intervals as appropriate for the treatment dose
Grade 3	Discontinue infusion immediately Administer supportive treatment Upon symptom resolution, may resume infusion rate escalation, at the investigator's discretion Treatment must be permanently discontinued, if same adverse event recurs with same severity.
Grade 4	Discontinue infusion immediately Treat symptoms aggressively Do not restart obinutuzumab

Reductions in obinutuzumab dosing are not planned. Repeat obinutuzumab administrations may be delayed to allow subjects to recover from obinutuzumab-related AEs or intercurrent illness.

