5.4.5. Prior and Concomitant Medications with Obinutuzumab

In accordance with current obinutuzumab prescribing information, subjects should be premedicated with an antipyretic and an antihistamine to reduce the incidence and severity of infusion reactions. A recommended regimen is diphenhydramine, 25 to 50 mg orally, and acetaminophen (paracetamol) 650 to 1000 mg orally, both given approximately 30 minutes prior to each obinutuzumab administration. In addition, an intravenous corticosteroid should also be administered as a premedication on Days 1, 2, 8, and 15 for all subjects, completed at least 1 hour prior to administration of obinutuzumab, and then only as indicated per the prescribing information. Local practices and guidelines may be followed.

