2. Screening and End of Treatment will be complete physical examinations. Beginning at Week 1 Day 1, a modified physical examination will be a performed to monitor for any changes (eg, lymph nodes, size of the liver and spleen, lung, cardiac, abdomen, skin, neurologic, and any system clinically indicated). Weight should be measured at each PE. Height should be measured at screening only.
3. The G8 screening questionnaire will be used for assessment of subjects aged > 70 years at Week 1 Day 1 and every 6 months until EOT.
4. Subjects should be resting quietly in supine position for 5 minutes prior to ECG collection. The Investigator or qualified designee will review all ECGs.
5. Study drug is not dispensed at the Week 105 visit.
6. Obinutuzumab: 100 mg will be administered intravenously on Day 1 and 900 mg on either Day 1 or 2 (Week 1); then 1000 mg on Day 8 (Week 2), Day 15 (Week 3), and on Weeks 5, 9, 13, 17 and 21 for a total of 8 doses of 1000 mg over 21 weeks. If the 100 mg infusion on Day 1 is well tolerated, the remaining 900 mg (scheduled for Day 2) may be given on Day 1.
7. CBC with differential should be obtained every 2 weeks through Week 25 to evaluate for neutropenia and then at subsequent visits for assessment.

8. Peripheral blood MRD will be assessed on Day 1 of Weeks 1, 13, 25, 33, 45, 105, and EOT. EOT collection is not needed for subjects who complete the Week 105 visit.
9. Serum pregnancy test will be performed at screening for all women of childbearing potential (defined in [Appendix 4](#)). Urine pregnancy tests will be conducted prior to Week 1, Day 1 and then every 4 weeks until the EOT visit. Pregnancy kits may be provided for home testing. The results must be confirmed as negative prior to continued administration of study drug.
10. Hepatitis serology includes HBsAg, HBcAb, HCV Ab; patients with positive HBcAb and negative HBsAg should have HBV DNA PCR performed prior to treatment start to rule out occult infection, then monthly through 6 months and then at subsequent clinic visits until EOT visit. HIV testing and CMV IgG and IgM testing should be performed at screening.
11. CMV antigen or quantitative PCR testing should be performed at screening and according to the schedule of assessments throughout the course of idelalisib treatment.
CCI [REDACTED]
- CCI [REDACTED]

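### Sections 5.3.2 and 5.4.5 of the protocol give different corticosteroid premedication rules for the Day 8 and Day 15 obinutuzumab infusions, and the trigger sentence in 5.3.2 is ambiguous

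*Protocol*

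**What the plan says.** Two protocol sections set steroid premedication for obinutuzumab.

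Section 5.3.2 requires an intravenous steroid, unless contraindicated, before the first dosage (Day 1, and Day 2 if the dose is split). Under its heading for subsequent infusions it says "A corticosteroid should be administered for premedication if the patient experienced a Grade 3 IRR during the previous infusion". It then adds, after a comma, a lymphocyte count above 25,000/µl, and closes the list with "and at the investigator's discretion". The list contains no *or*.

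Section 5.4.5 says "an intravenous corticosteroid should also be administered as a premedication on Days 1, 2, 8, and 15 for all subjects", "and then only as indicated per the prescribing information", and then permits local practice.

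Appendix 2, footnote 6, gives the schedule: Week 1, Day 8, Day 15, "and on Weeks 5, 9, 13, 17 and 21 for a total of 8 doses of 1000 mg over 21 weeks". Days 8 and 15 are therefore subsequent infusions in the sense of 5.3.2. Section 1.6, where it describes how obinutuzumab reactions will be mitigated, refers the reader to 5.3.2 for premedication and does not mention 5.4.5.

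On re-exposure, 5.3.2 says "Patients experiencing Grade 3 or 4 IRRs twice should receive aggressive symptomatic treatment and will be discontinued from further study treatment with obinutuzumab". It also stops obinutuzumab after a life-threatening, prolonged or recurrent reaction, and its grading table bars a restart after Grade 4.

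**The concern.** For the same two infusion days, one section calls for a steroid in everyone and the other only under conditions. A site that follows the pointer in Section 1.6 reaches the conditional rule and could omit a steroid that 5.4.5 calls for, while believing that it complies.

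The conditional rule is itself unclear. Taken at its word, *and* makes the conditions joint. A subject who had a Grade 3 reaction at the previous infusion but has a lower lymphocyte count would then not be called for a steroid, although a recent severe reaction is the first trigger listed.

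What is at stake is one subject's avoidable second reaction and, because a second Grade 3 or 4 event ends obinutuzumab, that subject's remaining doses of the drug that distinguishes Arm B. This is a matter of safety and of uniform conduct across about 25 centers.

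**Working it through.** No sample size, power or error rate is involved, so the check is a comparison of the texts.

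**Step 1: the Day 8 and Day 15 rules side by side.** Cross the two observable conditions in 5.3.2 and ask in which cells each text calls for a steroid.

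| Grade 3 reaction at previous infusion | Lymphocytes > 25,000/µl | 5.3.2 read with *and* | 5.3.2 read with *or* | 5.4.5 |
|---|---|---|---|---|
| Yes | Yes | Called for, subject to discretion | Called for | Called for |
| Yes | No | Not called for | Called for | Called for |
| No | Yes | Not called for | Called for | Called for |
| No | No | Not called for | Discretion only | Called for |

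Section 5.4.5 calls for a steroid in 4 of 4 cells. Section 5.3.2 does so in 1 of 4 read with *and*, and in 3 of 4 read with *or*. The sections therefore differ in 4 − 1 = 3 cells on the literal reading and in 4 − 3 = 1 cell on the lenient one. The inconsistency on these days does not depend on how the conjunction is read.

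**Step 2: which reading of 5.3.2 is likelier.** Investigator discretion makes little sense as a joint precondition to an instruction that a steroid *should* be given, so a loose list of alternatives was probably meant. Against that, the tumor-lysis paragraph of the same section writes *and/or* when it lists alternatives. The sentence is ambiguous, and the second row of the table is where the ambiguity matters.

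**Step 3: which infusions are involved.** There are 8 doses, so 8 − 1 = 7 follow the first. On 2 of these (Days 8 and 15) the sections conflict. On the other 5 (Weeks 5, 9, 13, 17 and 21), 5.4.5 states no trigger of its own and defers to the prescribing information. These are counts of scheduled infusions and do not measure risk.

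**Step 4: who could be affected.**

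- *At Day 8.* Section 1.4 reports that in the cited chlorambucil-combination trial most reactions came with the first infusion, and that 20% of obinutuzumab patients had Grade 3 or 4 reactions. If that pattern carries over to this population (an assumption), most prior Grade 3 reactors would meet the question at Day 8, where 5.4.5 already covers them if it is followed.
- *From Week 5.* All of the following must hold: a Grade 3 reaction on Day 15 or at Week 5, 9, 13 or 17 that is not life-threatening, prolonged or recurrent; lymphocytes at or below 25,000/µl at the next infusion; an investigator who reads *and* literally; and prescribing information that does not already call for a steroid. The documents give neither reaction rates by infusion nor lymphocyte counts over time, so the number cannot be estimated.

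**Step 5: effect on the analysis.** A subject who stops obinutuzumab after repeated reactions stays in: "Treatment with oral agents should be continued with the subject remaining on study". Protocol Section 8.2.1.1 and SAP Section 3.2 analyze the Full Analysis Set by assigned arm. The planned analyses are unchanged.

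**The case against.** The best reply is that a site can satisfy both sections at once. Section 5.3.2 never tells anyone to withhold a steroid, so giving one to every subject on Days 8 and 15 breaches nothing. Both sections say *should*, and 5.4.5 allows local practice. From Week 5, the prescribing information may already supply the trigger; Section 1.6 makes the obinutuzumab product summary the safety reference document. A Grade 3 reactor has other protection too. Paracetamol is given before every infusion, the antihistamine may not be dropped after a reaction above Grade 1, and infusions may be split over two days. Where the reaction came at the opening dose, "the administration may be per the guidance from the first infusion with a maximum rate that which has been previously tolerated by the subject".

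Most of this stands, and it limits the point. It does not remove it. A site reading only 5.3.2 would not learn that 5.4.5 wants a steroid for everyone on Days 8 and 15.

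Two stronger readings are tempting. A reader might infer that the protocol denies steroids to Grade 3 reactors. It does not: that follows only from the least plausible reading, and even then nothing prohibits a steroid. A reader might also infer that the gap runs through all five infusions from Week 5. The documents do not show this, because the prescribing information that governs there is not among them.

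**Conclusion.** The point holds as a minor inconsistency in supportive-care wording. On Days 8 and 15 the two sections differ under either reading of 5.3.2, and no text sets precedence. The *and* in 5.3.2 is a further drafting ambiguity that leaves out a Grade 3 reactor with lower lymphocytes only if taken literally. Whether anything is missing from Week 5 is unknown.

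The number of subjects affected is probably small. That judgment rests on the Section 1.4 statement that most reactions occur at the first infusion, and on the stopping rules, which remove subjects with Grade 4, life-threatening, prolonged or recurrent reactions before they could be re-exposed. A reader might infer that the complete remission rate in Arm B is compromised. The documents give no support for that: subjects who stop obinutuzumab continue oral treatment and remain in the primary analysis.

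**What to change.** In Section 5.3.2, replace the trigger sentence with two rules:

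1. Days 8 and 15: an intravenous corticosteroid for all subjects, as 5.4.5 already states.
2. From Week 5: an intravenous corticosteroid if any one of these holds: a Grade 3 reaction at the previous infusion, lymphocytes above 25,000/µl, or the investigator judges it needed.

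In Section 5.4.5, keep the rule for Days 1, 2, 8 and 15. Reword the clause that follows so that later steroids are guided by both the prescribing information and Section 5.3.2, without the word *only*.

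This removes no steroid that either section now calls for. The cost is one sentence and one clause, by protocol clarification or a note to sites, and a few additional single steroid doses. Sample size, visits and analysis do not change. If obinutuzumab dosing is already complete, the correction matters only where this text is reused.
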